Exclusion criteria (recruitment is not possible if any -at least one- criterion is met)	
 • Relevant comorbidity (with limitations to administer radiotherapy according to protocol) • Prior radiotherapy which results in limitations to administer radiotherapy according to protocol • No large metal implants in vicinity of lesion • Department dose constraints for normal tissue can't be met • Large bony lesions with extensive osseous destruction • Patients symptoms do not correlate with MR findings
Study therapy	
 • Image guided radiotherapy (IGRT) with hypo-fractionated simultaneous integrated boost (IMRT) • GTV1 = MR T2w lesion and ADC $\leq 1200 * 10^{-3}$ mm2/s • GTV2 = MR T2w lesion and ADC \leq median ADC in GTV1 • Each lesion is a CTV, CTV = GTV • PTV=CTV+ margin according to department standards • Dose-fractionation • CTV1: 4 x 5 Gy • CTV2: 4 x 7 Gy
Primary endpoint	Feasibility: Proportion of study participants that complete radiotherapy with $\geq 90\%$ of prescribed dose
Secondary endpoints	
 • Dominant symptom (VAS) • Progression-free survival >6 months • Overall survival

	
• Acute toxicity• Quality of life• Change in ADC from before to end of treatment• Change in ADC from before to 6 month post treatment
Sample size	34 patients has to be included in the study
Study sites	University Hospital Sjaelland, Naestved UKSH Campus Kiel UKSH Campus Luebeck
Time table	Recruitment period: 12 months Start of study: March 2018 End of study: March 2019 Follow-up: minimum \geq 6 months
Financing	Interreg (InnoCan)

3 Background and rationale

Prostate cancer is the major cause of cancer death in men living in developed countries. Large autopsy studies found that patients that presented prostate cancer demonstrated metastatic disease in 35% of cases. Prostate cancer metastases were 90% bone metastases, with 90% of the bone metastases involved the spinal cord, followed by lung (46%), liver (25%) and pleura (21%). Another important pathway is the lymphatic system, which is involved in 9 to 16% of cases, especially at the level of obturator, pre-sacral, internal, and common iliac arteries, and sometimes even the extra-regional para-aortic chains (1).

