10.2 Treatment planning

3D planning is mandatory. Type of treatment technique (e.g. 3D-IMRT, VMAT or SBRT) is the decision of the radiation oncologist. The reference MR scan (see appendix 2) must be co-registered to the planning CT and the target volumes defined on MR transferred to the planning CT for dose planning.

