10.3 Target volumes

Patients included in the study will be subjected to a protocol-specific MRI examination (see MR sequence and example of target delineation in appendix 19-20). A radiologist will read the MRI scan to validate correspondence between MR lesion and the patients dominating symptoms. In case of more than one lesion, decision on priority of target volumes will be made by the radiation oncologist based on clinical expertise. An ADC map will be calculated for the lesion using the DWI sequences. A cutoff ADC value of less than 1200×10^{-6} mm²/s in combination with a T2w image will be used to predict the MR lesion (GTV1) (26). The most aggressive part of the lesion (GTV2) will be defined using ADC of less than or equal to a cutoff value calculated as the median ADC value for the GTV1 (25). Notice that GTV2 need not to be one coherent volume, but may consist of several sub-volumes.

For the definition of target volumes, the following aspects should be considered: The clinical target volume (CTV) is the visible macroscopic tumor (GTV). The safety margin for the planning target volume (PTV) should be according to the department standard, and depending on the radiation technique used. The margin for the PTV2 for CTV2 may be chosen to be smaller than for PTV1 as this volume is enclosed in the CTV1, which receives a dose of 4 x 5Gy already.. For the treatment of breathing-dependent lesions (upper abdomen), treatment techniques with motion compensation (e.g. breath-hold or gating) should be used. All four fractions of the treatment should be given within two weeks of starting the radiotherapy.

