** SPIR = Spectral Presaturation with Inversion Recovery

*** b0 images and three b-values: b=50, 500 og 900 sec²/mm

[figure not shown]
Fat suppression should be preferably be done with a selective method as SPIR if possible. If not the STIR method, less specific, alternative method to use. Some post processing of MR images may be necessary to suppress noise in the images before automatically outlining the GTV. The ADC map should be calculated using all three b-values and mono-exponential fitting.

21 Appendix 3 - Target outline procedure

[figure not shown]
The following example demonstrate the target outline procedure on the MR images. This example is a reconstruction based on images from (28)

The target is outlined on the T2W image. This image is co-registered to the ADC map and the outline is transferred to the ADC map.

The outline transferred to the ADC map is subsequently corrected using a threshold for the $ADC < 1200 \text{ mm}^2/\text{s}$ for the target. This target is named GTV1

The median ADC value for the GTV1 target. The median value is used as threshold to obtain the most aggressive part of the target. This subvolume is named GTV2.

22 Appendix 4 – Flowchart for the study

	Inclusion	Visit 1 Baseline before RT	After RT	Visit 2 1 month	Visit 3 3 month	Visit 4 6 month
Screening / Inclusion	X					
Informed Consent	X					
Medical history	X					
MR scanning		X		X		X
Anamnesis		X				
Medical examination		X	X	X	X	X
Local Symptoms		X	X	X	X	X
Quality of Life		X				X
Toxicity		X	X	X	X	X
LPFS			X	X	X	X
ADC Response			X			X
Survival			X	X	X	X
AE/SAE			X	X	X	X
Concomitant medication		X	X	X	X	X
VAS		X	X	X	X	X
ECOG		X	X	X	X	X

23 References:

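### The ADC cutoff that defines GTV1, and through its median the GTV2 boost volume, is printed on inconsistent scales; only the section 10.3 value works as a cutoff in mm²/s

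*Protocol*

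**What the plan says.** The cutoff for GTV1 appears in three places in the Protocol, each time with the number 1200 and the unit mm²/s.

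- **Section 2, Synopsis, study therapy:** "GTV1 = MR T2w lesion and ADC $\leq 1200 * 10^{-3}$ mm2/s".
- **Section 10.3, Target volumes:** "A cutoff ADC value of less than 1200" × 10^-6 mm²/s, combined with the T2w image.
- **Section 21, Appendix 3 (worked example):** the T2w outline, once transferred to the ADC map, "is subsequently corrected using a threshold for the $ADC < 1200" mm²/s. No power of ten is printed in the text as read from the PDF.

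GTV2 depends on GTV1. Section 10.3 takes the voxels at or below "a cutoff value calculated as the median ADC value for the GTV1", and Appendix 3 repeats the rule. Section 10.4 prescribes 20 Gy in total to PTV1 and 28 Gy to PTV2.

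Appendix 2 (section 20) sets the acquisition: "b0 images and three b-values: b=50, 500 og 900 sec", with an ADC map from a mono-exponential fit. It also refers to post-processing "before automatically outlining the GTV". Section 10.2 has "the target volumes defined on MR transferred to the planning CT for dose planning".

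**The concern.** The unit is the same in all three places, so the printed values cannot be reconciled as one quantity in different units. The synopsis value is 1,000 times the section 10.3 value, and the Appendix 3 value as printed is 1,000,000 times it. The Protocol does not say which text governs, and it does not state the scale of the ADC map to which the number is applied.

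The number places dose. It decides which part of the T2w outline receives 20 Gy and, through the median, which part receives 28 Gy. Appendix 2 foresees automatic outlining, so a user is likely to type the threshold into software. Three sites plan separately, and section 10.5 leaves quality assurance to institutional standards. The adjudication committee in section 14 receives the treatment plans, but its stated task is to date the end of progression-free survival, not to check contours. If sites applied different thresholds, the volume and ADC comparisons in section 11.5 would rest on differently defined contours.

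**Working it through.** **Inputs.** Cutoffs in mm²/s: section 10.3, 1200 × 10^-6 = 0.0012; synopsis, 1200 × 10^-3 = 1.2; Appendix 3, 1200 as printed. The b-values 50, 500 and 900 and the mono-exponential model come from Appendix 2. I read b in s/mm², the unit that makes b × ADC dimensionless.

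**Step 1: can each value act as a cutoff?** The share of signal left at a given ADC is S(b)/S(0) = exp(-b × ADC).

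| Cutoff (mm²/s) | b = 50 | b = 500 | b = 900 |
|---|---|---|---|
| 0.0012 (section 10.3) | exp(-0.06) = 0.942 | exp(-0.6) = 0.549 | exp(-1.08) = 0.340 |
| 1.2 (synopsis) | exp(-60) = 8.8 × 10^-27 | exp(-600) = 2.7 × 10^-261 | exp(-1080), effectively 0 |
| 1200 (Appendix 3) | exp(-60000), effectively 0 | effectively 0 | effectively 0 |

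At 0.0012 the signal is measurable at every b-value, so voxels fall on both sides of the cutoff. At 1.2 or 1200 nothing measurable is left even at b = 50. Every voxel with measurable signal therefore lies below those values, and neither removes any voxel.

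**Step 2: effect of a literal reading in mm²/s.** Let V be the T2w outline and f the share of its voxels with ADC at or above 0.0012. GTV2 is the lower half of GTV1.

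- Section 10.3: GTV1 = (1-f)V and GTV2 = (1-f)V/2.
- Synopsis or Appendix 3, read literally: GTV1 = V and GTV2 = V/2.
- Ratio for both volumes: 1/(1-f). Extra boost volume: V/2 - (1-f)V/2 = fV/2.

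The Protocol gives no value for f. As assumed values for illustration:

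| f (assumed) | GTV1 and GTV2 enlarged by | Extra share of outline in GTV2 |
|---|---|---|
| 10% | 1/0.9 = 1.11 | 5% |
| 20% | 1/0.8 = 1.25 | 10% |
| 30% | 1/0.7 = 1.43 | 15% |

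These ratios do not depend on the shape of the ADC distribution, but their size depends wholly on f. As a second illustration, assume log-normal voxel ADCs with log-SD 0.3 and a median of 900, 1100 or 1300 × 10^-6 mm²/s. The section 10.3 cutoff then keeps 83%, 62% or 39% of the outline, so f is 17%, 38% or 61% and the ratio is about 1.2, 1.6 or 2.6. The direction is firm; the size is not known.

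**Step 3: dependence on map scale.** On a map stored in units of 10^-6 mm²/s, typing 1200 reproduces the section 10.3 cutoff exactly. On that same map the synopsis value, typed as 1.2, would leave GTV1 almost empty. What the printed number does therefore depends on a scale that the Protocol does not state.

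**Step 4: b-value unit.** The b-value unit in Appendix 2 reads as s²/mm. With ADC in mm²/s, b × ADC is dimensionless only if b is in s/mm².

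**The case against.** The strongest reply is that the Protocol already shows the intended value. Section 10.3 is the operative target definition, prints the workable number and cites a reference for it. The synopsis is a summary, and Appendix 3 presents itself as an example. A reader of section 10.3 would probably apply the right cutoff. This stands, and it limits the practical risk. It does not remove the contradiction between two explicit powers of ten in the synopsis and section 10.3.

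Second, the bare 1200 in Appendix 3 is right on a map scaled in 10^-6 mm²/s. This also stands. A silent enlargement needs a map in mm²/s and a user who disregards section 10.3. Even then, a correction step that removes nothing, or on another scale removes nearly everything, might well be noticed.

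Third, reading the PDF by program may have lost the factor in Appendix 3 and moved the superscript in the b-value unit. Neither can be excluded, so the point is anchored on the synopsis against section 10.3, and those two items are only to be checked. The difference between ≤ and < is immaterial for a near-continuous ADC.

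A reader might go further and infer that patients were irradiated to wrong volumes, or that the feasibility result is compromised. The document supports neither. It does not show which value any site used. Before margins, no target extends beyond the T2w outline, a radiologist reads each scan, and organ-at-risk constraints apply whatever the threshold.

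**Conclusion.** The point holds as an inconsistency in a parameter that places dose. The synopsis is wrong as written: its cutoff, taken in the unit printed, cannot exclude any voxel. Appendix 3 has the same defect if its missing factor is real and the map is in mm²/s. Section 10.3 carries the only value that works in the printed unit.

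If the wrong scale were used literally, GTV1 would become the uncorrected T2w outline and GTV2 would grow with it, both by 1/(1-f). No figure for f is available, so no size can be claimed. The conclusion about which value works rests only on the Protocol's b-values, its mono-exponential fit and b in s/mm².

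The primary endpoint is the proportion of patients completing at least 90% of the prescribed dose. Neither it nor the sample size or error rates are affected. The volume and ADC endpoints are touched only through the contour. Severity is minor to should-fix: the intended value is clear from section 10.3, but the figure sets the 20 Gy and 28 Gy volumes and is cheap to correct.

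**What to change.** - Print 1200 × 10^-6 mm²/s with one inequality sign in the synopsis, section 10.3 and Appendix 3.
- State the ADC map scale to which the number applies, for example that 1200 is entered on a map in 10^-6 mm²/s.
- Check in the source file that the b-value unit in Appendix 2 reads s/mm², and correct it if it does not.
- Before volume and ADC data are pooled, have each of the three sites confirm the numeric threshold and map scale it used.

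The cost is a few wording changes and one confirmation per site. No new scans, data or analyses are needed.
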